## 12.5 Analysis of Secondary Objectives

As support for the primary objective, overall DFS and 2-year DFS will be compared using the same techniques above using only the subjects in the randomized part of the study. One-year DFS will be tested using the test described above for 2-year DFS. Safety and tolerability variables will be tabulated separately for the two groups. Incidences of selected adverse events from the two treatment arms may be compared using Fisher's Exact tests on an exploratory basis. OS will be compared between treatment groups using the same methodology as DFS. PK levels will be described using summary statistics. In addition, characteristics of tumor specimens, and genomic DNA will be correlated with PARP inhibition, recurrence and toxicity. Continuous measures will be correlated with binary variables (e.g. recurrence and toxicity) using maximal chi-

square tests and continuous variables (e.g. PARP inhibition) using Pearson or Spearman correlations. Binary variables such as tumor and genomic characteristics will be correlated recurrence and toxicity using chi-square or Fisher's Exact test. All of the analyses with the PK and correlative data are exploratory and are designed to complement efforts in other trials with this agent.

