**Arm A**

Cisplatin 75 mg/m^2 IV D1 every 3 weeks x 4 cycles

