**Safety Run-in and Arm B**

Cisplatin 75 mg/m^2 IV D1 every 3 weeks x 4 cycles rucaparib 16-30 mg IV D 1,2,3 every 3 weeks x 4 cycles

Rucaparib maintenance 30 mg IV weekly OR 100 mg orally once weekly x 24 week's total

D Rucaparib will be escalated from 24mg to 30mg during the treatment phase of the study.

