### Rucaparib maintenance therapy for Safety Run-in and Arm B

**Table 5: Treatment plan – IV maintenance therapy**

**NOTE:** All patients should proceed with oral rucaparib for maintenance therapy after approval of Amendment #5 and when oral drug available.

Drug	Dose	Frequency of administration	Route of administration	Number of weeks
Rucaparib	30mg I	Weekly II	IV *	24

**\*NOTE:** 30 mg dose: ~34 minute infusion time, ~124 mL infusion volume. Volume calculated using an assumed standard overfill of 9 mL in a 100 mL commercial bag of D5W plus the required volume of reconstituted drug product for a specific dose.

**I:** Patients receiving  $\leq 30$  mg during combined therapy should begin maintenance therapy with 30 mg weekly.

**II:** The first week of maintenance therapy should begin 3 weeks after Day 1 of the last cycle of combination therapy unless a delay is required to allow recovery from toxicity.

**NOTE:** Patients unable to initiate maintenance therapy within 6 weeks after day 1 of the last cycle of combination therapy should discontinue protocol treatment.

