**Randomized Phase II – Arm A**

	Screening		Cycles 1-4	Post-treatment	Follow-up
	-30 days	-14 days	D1  (+/-3 days)	30-60 days from last treatment	+/-1 month
REQUIRED ASSESSMENTS					
Medical history	X				
Height	X				
Physical examination	X		X	X	X 
BP, weight	X		X	X	X 
ECOG performance status	X		X	X	X 
Blood Chemistries 		X	X	X	
Calculated creatinine clearance		X	X	X	
Platelets, ANC & Hgb		X	X	X	
Breast imaging					yearly
Electrocardiogram 	X		X		
MUGA or Echocardiogram	X				
Urine pregnancy or serum HCG 		X			
Adverse event and concomitant medication assessment	X		X	X	
TREATMENT					
Cisplatin			X		
CORRELATIVE STUDIES					
Tumor from diagnosis -Optional	X				
Tumor from definitive surgery -Mandatory	X				
Genomic DNA - Optional			X 		

1. Screening values obtained within 7 days of Day 1 do not need to be repeated prior to cycle 1 day 1.

2. Serum chemistries (creatinine, glucose, total protein, blood urea nitrogen [BUN], total carbon dioxide [CO2], albumin, total bilirubin, alkaline phosphatase, and aspartate transaminase [AST] and alanine transaminase [ALT]) and electrolytes (total calcium, chloride, potassium, sodium).

3. ECG will be done at baseline and prior to cycle 3. Additional ECG monitoring should be considered in patients who develop clinical significant electrolyte abnormalities during cisplatin therapy at the discretion of the treating physician.

4. Only in women of child bearing potential

5. If the genomic sample collection is missed at cycle 1 day 1, it can be collected at any time point during the study.

6. Every 4 months throughout years 1-2, then every 6 months for years 3-5.

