### 7.3 IV MAINTENANCE THERAPY

- During maintenance therapy patient will have weekly BP and weight along with study drug
- Every 4 weeks they need:
  - Physical examination
  - ECOG Performance status
  - Platelets, ANC, Hgb
  - Complete metabolic profile (CMP) including: serum chemistries (creatinine, glucose, total protein, blood urea nitrogen [BUN], total carbon dioxide [CO2], albumin, total bilirubin, alkaline phosphatase, and aspartate transaminase [AST] and alanine transaminase [ALT]) and electrolytes (total calcium, chloride, potassium, sodium)
  - Assessment of adverse events and concomitant medications
- PK levels: Plasma to be collected prior to infusion and 5 min (+/- 5 minutes) prior to the end of infusion during Week 1 and Week 5

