## **11.2 Adverse Event (AE) Reporting**

Adverse events (AEs) will be recorded from the time of consent and for at least 30 days after treatment discontinuation, regardless of whether or not the event(s) are considered related to trial medications. All AEs considered related to trial medication will be followed until resolution, return to baseline, or deemed clinically insignificant, even if this occurs post-trial.

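### Exploratory Fisher tests of adverse-event incidence set a short Arm A window against an Arm B window about 2.2 to 3 times as long, which biases the comparison against rucaparib for events that keep arising after chemotherapy

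*Combined protocol and SAP*

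**What the plan says.** Section 12.5 promises safety tabulations by group and then adds: "Incidences of selected adverse events from the two treatment arms may be compared", by Fisher's exact test and as an exploratory step. It gives no event list, significance level or time window. The general safety set in Table 13 is everyone who received at least one dose, with no time limit. No exposure-adjusted rate or time-to-event method for adverse events appears anywhere in the document.

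The treatment periods differ by design. The Schema gives Arm A "Cisplatin 75 mg/m 2 IV D1 every 3 weeks x 4 cycles". Arm B receives the same four cycles with rucaparib and then "Rucaparib maintenance 30 mg IV weekly OR 100 mg orally once weekly x 24 week's total". Table 5 fixes the planned start: "The first week of maintenance therapy should begin 3 weeks after Day 1 of the last cycle of combination therapy".

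The recording rule follows treatment. Section 11.2 states: "Adverse events (AEs) will be recorded from the time of consent and for at least 30 days after treatment discontinuation". In the Arm A calendar of section 7.0 the last visit with an adverse-event assessment falls "30-60 days from last treatment", and the follow-up column has none. During maintenance, sections 7.3 and 7.4 require "Assessment of adverse events and concomitant medications" every 4 weeks.

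**The concern.** A test on the proportion of patients who ever had an event treats the two arms as equally exposed to being counted. Here they are not. For about six months Arm B patients are on maintenance and being asked about adverse events, while Arm A patients have left adverse-event recording. Background events such as infection, pain or fatigue go on being counted in Arm B and cease to be counted in Arm A.

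The number of scheduled enquiries differs too. After screening, Arm A has 4 + 1 = 5 assessments and Arm B has 4 + 6 + 1 = 11.

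Side effects and tolerability come first among the secondary objectives, and this is the plan's only between-arm test of adverse events. If it is run as written, an excess in Arm B could be read as toxicity added by rucaparib when part or all of it reflects longer observation.

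**Working it through.** The plan states no figure for this comparison, so there is none to reproduce.

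**Observation windows** (cycle 1 day 1 = day 1, planned schedule)
- Last cisplatin dose: 1 + 3 × 21 = day 64.
- First maintenance dose: 64 + 21 = day 85. The 24th weekly dose: 85 + 23 × 7 = day 246.

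| Rule for the end of the window | Arm A (days) | Arm B (days) | Ratio |
|---|---|---|---|
| Last dose + 30 days | 94 | 276 | 2.94 |
| End of planned treatment period + 30 days | 84 + 30 = 114 | 252 + 30 = 282 | 2.47 |
| Last dose + 60 days | 124 | 306 | 2.47 |
| Last dose + 60 days, plus 14 to 30 days from consent (assumed) | 138 to 154 | 320 to 336 | 2.32 to 2.18 |

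The ratio is therefore about 2.2 to 3.

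**Inputs that are inferred or assumed**
- Arm size: (135 − 12 run-in) / 2 ≈ 61, taken as 60. Equal allocation is inferred from section 12.3, which expects about 20 from each group among the first 40 randomized.
- Significance level: two-sided 5%. Section 12.5 gives none.
- Arm A incidence pA: 10% or 20%.
- r: the background hazard during maintenance as a share of the hazard in the earlier period. The documents give no value, so a range is shown.

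**Formula.** With no rucaparib effect and window ratio k, the Arm B incidence is pB = 1 − (1 − pA)^(1 + r(k − 1)). Example with pA = 10%, k = 2.94, r = 1: 1 − 0.9^2.94 = 26.6%. The rejection probability is the sum of the products of the two binomial probabilities over all outcome pairs for which Fisher's p-value is at most 0.05.

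**Results, 60 per arm.** Each cell gives pB, then the probability of rejection.

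| r | pA 10%, k 2.47 | pA 10%, k 2.94 | pA 20%, k 2.47 | pA 20%, k 2.94 |
|---|---|---|---|---|
| 1 | 22.9%, 39% | 26.6%, 58% | 42.4%, 70% | 48.1%, 87% |
| 0.5 | 16.7%, 12% | 18.7%, 19% | 32.1%, 26% | 35.5%, 40% |
| 0.25 | 13.4%, 5% | 14.5%, 7% | 26.3%, 9% | 28.2%, 13% |
| 0 | 10%, 2% | 10%, 2% | 20%, 3% | 20%, 3% |

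**Sensitivity, at r = 1**
- At k = 2.19, near the low end of the range, pB is 20.6% and 38.7%, and the test rejects 27% and 54% of the time.
- Suppose only half of Arm B has the full window (k = 2.94) and the rest have Arm A's. Then pB = 0.5 × 26.6% + 0.5 × 10% = 18.3%, and the test rejects 18% of the time. For pA = 20%, pB is 34.0% and the test rejects 33%.

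The row r = 0 also shows what a common window gives: 2-3%, below the nominal 5% because Fisher's test is conservative.

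**The case against.** **The test is optional and exploratory.** Section 12.5 says only that selected incidences may be compared. No decision hangs on the result, and the objective is to characterize side effects, which tabulation serves. This limits the importance. It does not remove the problem: an exploratory label warns about multiplicity, whereas unequal observation shifts the estimated difference itself.

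**Maintenance is part of the Arm B regimen, so its whole burden matters.** That is fair. But comparing that burden with Arm A needs Arm A observed over the same calendar period, and it is not.

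**The high rejection rates need a constant hazard.** This stands. A reader might infer that the test misleads for any adverse event, or that the 39-87% range is what to expect. The documents do not support that. Section 10.2.10 describes vomiting lasting 24 hours, with symptoms for up to a week. Section 10.2.9 puts blood-count nadirs at days 18 to 23, with most patients recovered by day 39. Section 10.1.5 names a mild injection site reaction as the main event due to rucaparib alone. For toxicity tied to the cisplatin doses the test keeps its level.

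**Two further readings go too far.** Recording does not stop at exactly 30 days, since section 11.2 sets a minimum. Nor do background events accrue in Arm B only: they accrue in both arms, for longer in Arm B. Also, section 12.3 tabulates toxicity by arm after two cycles, which is close to a common window, though only for the first 40 randomized patients and without a test.

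**Conclusion.** The point holds for events that continue to arise at a material rate after chemotherapy. For those, the comparison allowed in section 12.5 is biased against rucaparib, because Arm B is observed about 2.2 to 3 times as long as Arm A and nothing in the plan corrects for it. The size depends mainly on the background hazard during maintenance, which the documents do not give, so the chance of a false signal runs from the test's own 2-3% up to 87% over the values examined. The arm size, the 5% level and the Arm A incidences are inferences or assumptions, and early stopping in Arm B would reduce the effect. The primary analysis, sample size and safety stopping rules are unaffected. The importance is minor to moderate.

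**What to change.** In section 12.5, and in the matching synopsis text:
- Restrict any between-arm Fisher comparison to one fixed window defined identically in both arms, for example cycle 1 day 1 to 21 days after the last cisplatin dose, when maintenance is due. The 30-day minimum for recording covers this in Arm A.
- Do not end the window at each patient's actual first maintenance dose. Tables 5 and 6 let that dose be delayed for toxicity, so the window would depend on the outcome, and Arm A would have no matching day.
- Tabulate maintenance-phase events for Arm B alone.
- Give whole-period results by arm as events per patient-month.

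The cost is a few sentences and one or two extra tables. The analysis needs event onset dates. The protocol leaves case report form detail to the Study Procedures Manual, so their collection should be confirmed there. The drawback is that events after the common window are described and not tested. No change to treatment, sample size or the primary analysis is needed.

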## 7.7 FOLLOW-UP:

- Patients will be monitored by their treating physicians for the development of either local (chest wall, axillary, or supraclavicular nodes) or distal recurrent disease at least once every 4 months for the first two years, then at least every 6 months during years 3-5 after randomization.
- Suggested guidelines for surveillance of breast cancer survivors are available through the National Comprehensive Cancer Network ([www.nccn.org](http://www.nccn.org)).
- Routine blood work or radiology in the absence of symptoms suggestive of recurrent disease is not recommended.
- Remaining breast tissue (contralateral breast and ipsilateral breast in patients treated with breast conserving surgery) should be imaged annually according to standard screening guidelines.

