### **12.1 Sample Size Justification**

The primary endpoint for this trial is 2 year DFS. In order to detect an improvement of the fraction of patients free from disease at 2-year from 40% in the control arm to 63.2% in the rucaparib arm (corresponding to an HR=0.5), 38 events are needed to have 80% power to detect a difference in DFS using a one-side log-rank test with 0.10 level of significance (calculation done using nQuery Advisor 7.0 and assuming exponential survival). In order to observe 38 events we need to accrue about 102 patients, with an accrual time of about 13-18 months and an overall study duration around 25-30 months. In addition, 6 patients will be needed at the lower dose (cohort 1). Assuming ~20% will not be confirmed to have TNBC on central review; the total sample size will be increased to 135 to ensure 102 in the primary analysis (using cohort 2 and the randomized patients) and 6 in the safety analysis for cohort 1.

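### Exploratory marker analyses treat recurrence as yes/no under unequal, censored follow-up; testing the markers against DFS as a time-to-event endpoint would usually be better at almost no cost

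*Combined protocol and SAP*

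**What the plan says.** Section 12.5 (repeated in the synopsis) sets the tests. For continuous markers: "Continuous measures will be correlated with binary variables (e.g. recurrence and toxicity", by maximal chi-square tests. For binary markers: "Binary variables such as tumor and genomic characteristics will be correlated recurrence and toxicity using chi-square or Fisher's Exact test". The section gives no landmark time for recurrence, no minimum follow-up, no data cut, and no rule for a patient censored without recurrence. It also states: "All of the analyses with the PK and correlative data are exploratory".

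Follow-up will differ between patients. Section 12.1 plans the trial "with an accrual time of about 13-18 months and an overall study duration around 25-30 months". Section 7.7 then has patients monitored "at least once every 4 months for the first two years, then at least every 6 months during years 3-5 after randomization". Section 7.5 lets patients withdraw consent to further follow-up.

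Elsewhere the plan keeps the time dimension. Section 8.0 defines DFS as a duration, Section 12.4 compares it by Kaplan-Meier and log-rank, and Section 12.5 treats overall survival the same way. Section 12.4 also permits, without requiring, Cox regression to look for prognostic factors, but does not name the tissue or DNA markers.

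**The concern.** Under a yes/no coding, a patient censored event-free at 8 months counts the same as one event-free at 5 years. This has two possible consequences. First, information already collected is discarded, which usually costs power. Second, if length of follow-up is related to the marker, the group followed longer has more chance to show a recurrence, and the test can report an association that does not exist. Exploring correlates of recurrence is a listed secondary aim (Section 2.2), and Section 12.5 intends the results to complement work in other trials. A missed or spurious marker could therefore be carried forward.

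**Working it through.** **The plan's own figure.** HR = ln(0.632)/ln(0.40) = 0.501. Events (Schoenfeld, one-sided 0.10, 80% power, 1:1) = (1.2816 + 0.8416)² / (0.25 × (ln 0.5)²) = 37.5, so 38, as stated in Section 12.1. The plan gives no power or error figure for the marker analyses.

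**Spread of follow-up.** The last patient has study duration minus accrual: from 25 − 18 = 7 months to 30 − 13 = 17 months. The first has 25–30 months. The spread equals the accrual time, 13–18 months.

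**Hazard.** Control: −ln(0.40)/24 = 0.0382 per month. Rucaparib: half of that, 0.0191. Average: 0.0286. With uniform accrual over A months and analysis at T, P(event) = 1 − [e^(−λ(T−A)) − e^(−λT)]/(λA). For 18/30 this is 0.543 and 0.327, or 44.3 events in 102 patients. Over the plan's ranges it gives 36.0–48.3 events, which contains 38.

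**Comparison.** Trials of 102 patients were simulated at the average hazard, and both tests were applied to the same data at two-sided 5%. Marker prevalence, marker HR, loss to follow-up and calendar drift are assumptions; the documents give none.

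Power, %:

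| Accrual/analysis (months) | Marker | Yes/no chi-square | Log-rank |
|---|---|---|---|
| 13/25 | HR 2, 50% | 55.8 | 57.3 |
| 18/30 | HR 2, 50% | 59.4 | 60.9 |
| 18/25 | HR 2, 50% | 50.5 | 52.4 |
| 13/25 | HR 2, 20% | 46.2 | 52.6 |
| 18/30 | HR 2, 20% | 47.5 | 55.1 |
| 18/25 | HR 2, 20% | 42.4 | 48.8 |
| 18/30 | HR 0.5, 20% | 36.4 | 32.9 |
| 24/60, constant hazard | HR 2, 50% | 77 | 83 |
| 24/60, constant hazard, 1% monthly loss | HR 2, 50% | 62 | 76 |
| All followed 60 months, constant hazard | HR 2, 50% | 77.8 | 86.8 |
| All followed 60 months, constant hazard | HR 2, 20% | 44.9 | 75.4 |
| 24/60, hazard falls to a quarter after 24 months | HR 2, 50% | 73.6 | 74.9 |
| Same, 1% monthly loss | HR 2, 50% | 66.1 | 69.9 |
| 24/60, hazard falls to a tenth after 24 months | HR 2, 50% | 71.8 | 71.2 |

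Absolute powers move by a few points between simulation set-ups; the gap within a row is the figure to read. The 24-month accrual in some 5-year rows is longer than the plan's 13–18. It does not create the gap: with 18-month accrual and everyone followed for 60 months, the balanced-marker gap is 9 points.

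**Type I error, marker without effect.**
- Follow-up unrelated to the marker: about 5% for both tests, at either prevalence.
- Monthly loss of 1% in one marker group and 2–2.5% in the other: chi-square about 6–8% at 18/30. At 24/60 it is about 15% for 1% v 2% and up to 27% for 1% v 2.5%. Lower loss rates at the same ratio give less, down to around 10%.
- Marker prevalence drifting between the two halves of accrual, analysis at 25–30 months: 60/40 gives 5.6–6.6%, 70/30 gives 7.2–10.3%, 80/20 gives 10.5–17.6%.
- The log-rank test stayed at about 4–5% throughout. It allows censoring to differ between groups, provided that within a group censoring is unrelated to the event time.

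**The case against.** The strongest reply is that little hangs on these tests. They are labelled exploratory, no decision or error rate depends on them, and Section 12.4 already allows Cox regression for prognostic factors. This stands as a limit on importance. It does not settle the matter: the Cox option is discretionary, belongs to the primary objective and does not name these markers, while Section 12.5 prescribes chi-square-type tests for them.

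A reader might infer that unequal follow-up by itself creates false associations. The documents do not support that. When follow-up is unrelated to the marker, error stays near 5%. Inflation needs a link between marker and follow-up length, and the documents give neither such a link nor a loss rate. If everyone were followed for a full 5 years before testing, even 80/20 drift leaves error at 5.1%; but no such timing is fixed.

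A reader might also take the 5-year power gap as established. It depends on carrying the sample-size hazard, set for a 25–30-month study, forward unchanged to 5 years. If the hazard falls to a quarter after 2 years the gap is about 1 point (about 4 with 1% monthly loss), and at a tenth it disappears.

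Two further cautions hold. Genomic DNA is optional (Section 9.2), so 102 overstates the number available for DNA markers. And the simulated event rate is that of DFS, which counts deaths and second cancers as well as recurrence.

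**Conclusion.** The point holds as a cheap improvement to an exploratory analysis. Section 12.5 specifies a test that ignores time and censoring where the plan already has a time-to-event endpoint. Under an assumed marker HR of 2 and 102 patients, the usual cost is about 2 power points for a balanced marker and 6–8 for an adverse marker at 20% prevalence at 25–30 months. At 5 years it is about 6–15 points for a balanced marker under a constant hazard, and little or none if the hazard drops sharply after 2 years. The loss is not universal: for a protective marker at 20% prevalence it reverses by 3–4 points. False-positive error is a conditional risk: near 5% unless follow-up is related to the marker, about 6–8% at 30 months and 10–15% or more at 5 years under an assumed 2–2.5-fold difference in loss. Nothing here bears on the primary DFS comparison, and it should not be read as a criticism of it.

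**What to change.** In Section 12.5 and the matching synopsis text:
- Relate tumour and genomic markers to DFS as defined in Section 8.0, by Cox regression or a log-rank test, stratified or adjusted by arm. DFS is preferable to time to recurrence, which the documents do not define and which would need a rule for deaths and second cancers.
- Where a cut point is sought for a continuous marker, use a maximally selected log-rank statistic with its adjusted p-value.
- Keep chi-square or Fisher tests for toxicity.

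The cost is SAP wording and a little more analysis work, with slightly lower power in some rare-protective-marker cases. No new data are needed.

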## **13.0 TRIAL MANAGEMENT**

### **13.1 Quality Controls and Quality Assurance**

#### **13.1.1 Study Monitoring/Auditing**

Monitoring/Auditing visits to the trial sites will be made periodically during the trial, to ensure all aspects of the protocol are followed. Source documents will be reviewed for verification of agreement with data as submitted via the data collection system. The investigator/institution guarantee access to source documents by HOG or its designee and appropriate regulatory agencies.

The trial site may also be subject to quality assurance audit by Pfizer or its designee as well as inspection by appropriate regulatory agencies.

It is important for the investigator and their relevant personnel to be available during the monitoring/auditing visits and for sufficient time to be devoted to the process.

